#### 3. Study Procedures

*a.* Study design, including the sequence and timing of study procedures (distinguish research procedures from those that are part of routine care).

In summary, all participants will receive cognitive, language and detailed spelling evaluations as well as quality of life questionnaires. All participants will be chosen from [name] database, one of the largest PPA databases in the country and will be aware and have agreed to try to participate for the full length of the study, which may extend to three weeks for each experimental period. Then there will be a 2-week, 2-month and 6-month follow-up. Each participant will first be enrolled in the control condition for 12 weeks during which they will receive no intervention. They will receive language, cognitive and quality of life evaluations before and after this period. In this way they may serve as their own control and their own decline rate will be specified.

An additional group of 30 matched healthy controls will be recruited, mostly from the pool of spouses of participants in the tDCS study or matched controls from the Johns Hopkins community. They will be asked

to 1) participate in behavioral evaluations of the same language and cognitive assessments given to PPA and MCI participants, 2) wear actigraphs to assess sleep, and 3) have an MRI/MRS scan. Participation will occur at one time point and will be voluntary for any portion of the study.

#### Quality of Life questionnaires:

Participants will be administered standardized and non-standardized quality of life questionnaires before, after, and at follow-up intervals of each experimental period. The purpose of these questionnaires is to assess whether the proposed interventions have affected participants well-being and the general quality of their life.

#### Language Tasks:

Patients will be administered baseline language and cognitive tasks, including 1 or more of the following, depending on their residual language and cognitive skills: a) writing to dictation b) oral spelling c) oral and written naming of pictures d) word-picture matching f) written picture description g) digit span h) spatial span i) verbal learning

Language Therapy tasks:

#### Spelling

#### Treatment of the PGC mechanism (PGC intervention)

For the PGC intervention, patients will receive language therapy of either phoneme-grapheme correspondence (PGC) or study of particular words (lexical therapy) or other similar type of therapy depending on the particular spelling deficit of each patient. Up to 30 English sounds will be selected representing most common word-initial English phonemes (speech sounds). Then a set of up to 30 English words starting with these sounds will be used as prompts to help the participants relate each sound to a grapheme (abstract letter identity or sequence of letter identities). In the case of spelling therapy with words, sets of up to 50 English words with matched psycholinguistic characteristics (frequency, length etc) will be chosen and divided in sets for either baseline testing, training, homework, or repetition. In the case of PGC therapy, the participant will be either asked to provide the letters that would correspond to each sound and if failed to do so will be provided with word prompts. In the case of lexical therapy, the participant will be asked to spell the chosen words and if failed to do so will be taught the spelling of each word in the training set or proceed to the rest of the set in other sets. Words or PGCs will be taught in blocks of 10; when the patient reaches criterion (80% correct) he or she will continue to the other blocks. Individuals who reach criterion quickly will move to a second stage, in which they will be asked to write words beginning with each target phoneme. They will be assisted in correcting the spelling of the words by "sounding out" the word. Baseline evaluation before each therapy session will be held before each therapy session and will either require that the participant would choose--from a series of possible initial letters or letter sequences of English written in front of him or her--the letter or letter sequence that corresponds to the phoneme the examiner provides each time. Treatment of the lexical access mechanism (lexical access intervention).

For the lexical access treatment we will follow the methodology of the only other published spelling intervention in PPA (Rapp & Glucroft, 2009). Stimuli will consist of three word sets (n=10 for each set) that will be matched for lexical frequency, letter length, regularity, and concreteness. We will use 10 stimuli for each set to better match the PGC and lexical treatments. Set 1 will serve as trained items for the first condition (either sham or tDCS), and set 2 as untrained items and then set 2 will serve as trained items JHMIRB eFormA 01

and set 3 as untrained. A spell-study-spell procedure (Beeson et al., 2013; Rapp & Glucroft, 2009) similar to that used in a number of other studies will be applied to the trained words, such that at every training session the patient will be asked: (1) to spell each word to dictation, (2) to study the word presented on a written note card and orally name each of its letters while the experimenter repeats the word, and (3) if the word has been spelled incorrectly to attempt to spell it again. This procedure will be repeated until the words of each set are correctly spelled for two consecutive sessions. If a word is spelled correctly on the first attempt, the word will still be presented for the participant to study and only then will the experimenter continue to the next word. Untrained words will be presented for spelling to dictation only at the time of the pre- and post-treatment evaluations and at two follow-ups to evaluate whether therapy gains generalize to the spelling of other words.

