## Naming

Individuals with word-retrieval deficits will have naming therapy, using either or both of the following therapies, depending on their severity of deficit and how fast they meet criterion for progression to the next level (100% accuracy on all trained stimulus sets).

Level 1: Naming actions, objects, or people from pictures using a cuing hierarchy (Hillis, 1989) At each step, the participant attempts to retrieve the target word in response to a picture. If correct, the participant moves to the next picture after rehearsing the correct word multiple times. If incorrect, the participant is given the next cue.

- 1. Participant attempts to name target picture (for example, table).
- 2. Initial phoneme cue: "It starts with /t/."
- 3. Rhyme cue: "It sounds like fable."
- 4. Oral reading cue: Present word for oral reading.
- 5. Repetition cue: "Say table."

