#### Assessment

Follow-up assessment will probe all sets of trained phoneme-grapheme correspondences, words, or other stimuli (e.g. sentences) to identify whether or not the patient has retained knowledge of the trained items. We will look at generalization effects (i.e. effects of training to untrained items). Differences in baseline measures in pre- and post-therapy accuracy for phoneme-grapheme correspondences for each patient will be evaluated using chi-square or Fisher's exact tests.

Participants will receive approximately 3-5 therapy sessions per week for 1-3 weeks for each stimulation site. There will be 1-5 stimulation sites depending on the characteristics of each individuals and their availability.

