#### tDCS methods:

Participants will take part in 5-15 consecutive training sessions (3-5 per week), each with a different tDCS condition/site of stimulation (see Table 1) separated by 2 months. Three pre-training sessions separated by 2 weeks, each with a different tDCS condition/site of stimulation (see Table 1), may be proposed to pre-test the tDCS montages. Anodal tDCS has typically been shown to up-regulate neuronal excitability and produce enhancement of behavioral performance. We hypothesize that anodal cerebral tDCS applied during behavioral therapy will enhance the therapeutic outcome relative to the sham tDCS condition as measured by the change from pre- to post-treatment accuracy in the trained task (e.g. number of correctly learned grapheme-phoneme correspondences, correctly named pictures, correctly named words in a given category) for trained and untrained stimuli. Previous tDCS protocols for acquisition of eyeblink

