#### 6. Study Statistics

#### *a. Primary outcome variable.*

The primary outcome measures will be: a) change in performance from pre- to post-treatment levels on the trained items (e.g. change in % accuracy in phoneme-grapheme conversion of trained phonemes, % accuracy naming of trained pictures, average % correct names produced in trained categories in 1 minute), and, b) generalization to untrained items, measured by change in performance from pre- to post-treatment levels on the trained items (e.g. change in % accuracy in phoneme-grapheme conversion of untrained phonemes, % accuracy naming of untrained pictures, average % correct names produced in untrained categories in 1 minute). For those individuals with DLPFC stimulation for executive functions, we will use an additional automated score from BrainHQ program training (Smith et al., 2009). For individuals

receiving home-based tDCS over the left perisylvian areas and their right hemisphere homologs, we will assess pre- to post- language scores.

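### Trained items and naming level depend on on-treatment performance, but no scored list or level is fixed for the tDCS-sham contrast

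*Combined protocol and SAP*

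**What the plan says.** **Progression depends on performance in two therapy streams.**
- Section 3a, Treatment of the PGC mechanism: "Up to 30 English sounds will be selected representing most common word-initial English phonemes". Teaching is stepwise: "Words or PGCs will be taught in blocks of 10", and "when the patient reaches criterion (80% correct) he or she will continue to the other blocks". There is also a further step: "Individuals who reach criterion quickly will move to a second stage, in which they will be asked to write words beginning with each target phoneme".
- Section 3a, Naming: the therapy used depends on severity and on "how fast they meet criterion for progression to the next level (100% accuracy on all trained stimulus sets"). Level 1 is picture naming and Level 2 is generating words in categories, whose difficulty rises as the participant advances.

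**The outcome is described in two ways.**
- Section 6a gives a percentage: "change in % accuracy in phoneme-grapheme conversion of trained phonemes". It lists separate measures for naming pictures and for producing names in categories within a minute.
- Section 3a, tDCS methods, gives a count: "number of correctly learned grapheme-phoneme correspondences". Section 6c likewise defines change as the before-to-after difference in letter-sound associations learned, which reads as a number.

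**The probe set.** Section 3a, Assessment: "Follow-up assessment will probe all sets of trained phoneme-grapheme correspondences, words, or other stimuli".

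**Two streams are fixed.** Lexical-access therapy uses three matched sets of 10 words, allocated to periods in advance. Repetition therapy uses ten trained and ten untrained triplets. Neither adds items to the trained set by performance.

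**The concern.** Section 6c tests a within-patient difference, tDCS minus sham. That difference has a clear meaning only if both terms are measured on the same scale. In the PGC, block-taught word and naming streams, the number of items trained, or the task reached, follows from how fast the participant learned under that condition. Hypothesis 1a expects goals to be reached sooner with tDCS. If that is right, tDCS periods will tend to open more blocks and reach the category level more often, so the scale would shift with treatment exactly when treatment works.

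At stake are the size of the primary contrast and, in some patients, its direction. In naming, a difference could be formed between a picture score in one period and a category score in the other. The choice between a percentage and a count also stays open, and under this progression rule the two can rank the conditions differently.

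**Working it through.** **1. The plan's own figure.** Section 6c states 75% power for 30 participants, design effect 1.5 and effect size 0.8. Two-sided alpha 0.05 is assumed, because none is stated.
- 30 x 1.5 = 45 equivalent independent participants, or 22.5 per arm.
- 0.8 x sqrt(22.5/2) = 2.683, and 2.683 - 1.960 = 0.723. Normal power is 76.5%; the noncentral t gives 74.6%.
- The figure reproduces. It presumes an effect of 0.8 on an outcome whose scale is not yet fixed.

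**2. One pair of periods, three scoring rules.** From section 3a: blocks of 10, criterion 8 of 10, up to 30 sounds. Assumed: 2 of 10 correct at baseline in every block, and a 30-item list in each period. Sham stays in block 1 and ends at 7/10. tDCS ends at 9/10 in block 1 and 3/10 in block 2.

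| Rule | Sham | tDCS | tDCS - sham |
|---|---|---|---|
| % of items trained | 7/10 - 2/10 = +50 | 12/20 - 4/20 = +40 | -10 points |
| % of fixed 30 items | 11/30 - 6/30 = +16.7 | 14/30 - 6/30 = +26.7 | +10 points |
| Number learned | 5 | 7 + 1 = 8 | +3 items |

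The plan does not say whether one pool of sounds serves both periods. With a 20-item list the fixed-list contrast would be 3/20 = +15 points.

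**3. When a pair reverses.** With sham at 70% in one block and tDCS in two blocks with accuracies a1 and a2 (equal baselines), the trained-item contrast is negative when (a1 + a2)/2 < 0.7, that is a2 < 1.4 - a1. For a1 from 0.8 to 1.0, the bound on a2 runs from 0.6 down to 0.4.

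**4. Simulated progression under the 80% rule.** All learning rates are assumptions.
- *Full retention, equally hard blocks* (baseline 20%, 5-15 sessions, per-session learning rate 0.05-0.30, tDCS rate ratio 1.25-2). The mean contrast on trained items was always positive. It was often much smaller than on the fixed list: +4.0 against +10.4 points at 15 sessions, rate 0.08, ratio 1.5. This is not universal: at 15 sessions, rate 0.05, ratio 1.25, it was +3.7 against +3.2. The two rules disagreed in sign in 0-24% of individual pairs.
- *Wider grid* (baseline 0, 20 or 40%; forgetting of earlier blocks 0, 3 or 6% per session; later blocks equally hard or harder). The mean reversed in 59 of 1701 settings (3%): none of 567 without forgetting, 13 of 567 at 3% and 46 of 567 at 6%. The largest reversal was -5.9 points against +4.5 on the fixed list. The mean number learned was lower under tDCS (by more than 0.1 item) in 1 of 1701 settings.

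These are raw points, not standardised effects, so they do not convert directly into lost power.

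**5. Naming.** The two levels have different measures, so no common arithmetic applies. The plan does not say which level is scored after a switch, or which level the second period starts from.

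**The case against.** **The scored set is undefined, not wrong.** A reader might infer that scores will certainly be taken on different items in the two periods. No section says that the denominator is the opened blocks. Up to 30 sounds are selected, and word lists are divided into baseline, training and other sets, so a pre-set list is a plausible reading. The sentence in Assessment about probing trained sets concerns follow-up retention. This stands: the fault is that the plan leaves the scored set open. A pre-treatment score does not settle it, because section 3a also provides an evaluation before every session, from which a block could be baselined when it opens.

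**Reversal is not the usual result.** A reader might infer that a real benefit will commonly appear as harm. The simulations do not support that, and on the count in sections 3a and 6c reversal essentially does not occur. Examples must also respect the rule. If tDCS ends at 9, 8 and 5 of 10 and sham at 8/10 with only one block open, the contrast is 53.3 - 60 = -6.7 points, but 8/10 meets the criterion and should open block 2 unless it is first reached at the last probe. With sham at 7/10 the contrast is 53.3 - 50 = +3.3 points, against 53.3 - 16.7 = +36.7 on the fixed list. That is attenuation, not reversal.

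**Unopened items passing as untrained.** A reader might infer that the second primary outcome is contaminated. Nothing in the text says that unopened blocks fill the untrained list. Untrained material is set apart in lexical-access and repetition therapy, and untrained categories are kept out of naming training.

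**Scope.** Lexical-access and repetition therapy are unaffected. The PGC second stage keeps the same target phonemes, so the scored task need not change there. How often naming participants would reach 100% on all sets in 5-15 sessions is unknown.

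**Conclusion.** The point holds for PGC and block-taught word therapy and for naming therapy. Progression depends on performance under the assigned condition, and no section fixes one scored list or naming level for both periods.

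If section 6a is read as accuracy over the items actually trained, the usual effect is attenuation. Single pairs can reverse (-10 against +10 points in the example), and reversal of the mean is uncommon and needs forgetting of earlier blocks. These sizes rest on assumed baselines, learning rates and retention; the documents give none of them.

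A reader might also infer a false-positive problem. Under the strict null, progression does not depend on the treatment label, so the permutation test is not disturbed by this route. The issue is what is estimated, and its size and direction. The stated 75% power is not contradicted. The percentage in section 6a and the number in sections 3a (tDCS methods) and 6c must be reconciled in any case.

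**What to change.** Amend sections 3a, 6a and 6c as follows.

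1. Before randomisation, set for each participant and each period a matched list of items assigned to training, a separate untrained list, and the naming level used for the primary score.
2. Probe the full lists, and the pre-set naming level, before and after each condition. Score over the whole assigned list, whatever block or level was reached.
3. Report blocks opened and levels reached separately, as descriptive measures of speed.
4. State one primary metric and use it in sections 3a, 6a and 6c.

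Therapy can progress as now planned; only the scored set is fixed.

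**Cost.** Wording, plus extra probe items at evaluations that already take place. For a 30-sound PGC list this is up to 30 - 10 = 20 items. It may be more for word lists, which can run to 50, and for naming. If one pool of sounds has to supply both periods, the plan must say how it is divided. Including unopened items will also give smaller percentage gains in slow learners.

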## Naming

Individuals with word-retrieval deficits will have naming therapy, using either or both of the following therapies, depending on their severity of deficit and how fast they meet criterion for progression to the next level (100% accuracy on all trained stimulus sets).

Level 1: Naming actions, objects, or people from pictures using a cuing hierarchy (Hillis, 1989) At each step, the participant attempts to retrieve the target word in response to a picture. If correct, the participant moves to the next picture after rehearsing the correct word multiple times. If incorrect, the participant is given the next cue.

- 1. Participant attempts to name target picture (for example, table).
- 2. Initial phoneme cue: "It starts with /t/."
- 3. Rhyme cue: "It sounds like fable."
- 4. Oral reading cue: Present word for oral reading.
- 5. Repetition cue: "Say table."

#### Level 2:

Naming words in categories, given initial letters (after the game "Categories"). Participants will be given cards with category labels in rows, and initial letters as columns. The task will be to complete all cells as quickly as possible. The investigator/trainer will have "answer cards" and will be permitted to provide cues, allowing the participant half credit for each correct answer after cues. If the participant thinks of a word that is not on any of the answer cards he or she will get double "credit." Cards are organized by level of difficulty, so that the participant progresses to more difficult categories and initial letters over time, trying to maintain both credit (accuracy without cues) and time. All categories on these cards are considered "trained" categories. Untrained categories will not be used in this training. We will evaluate word generation/fluency (naming words in a given semantic category, as quickly as possible in 1 minute), for both trained and untrained categories.

#### Working memory/repetition therapy

For individuals with working memory/repetition deficits we will follow a treatment that features a repetition intervention, as used previously in the literature (Marangolo et al., 2011; McNeil et al., 1995; Murray, 2012; Sung et al., 2009). Participants will be trained in a series of words or sentences of increasing complexity, i.e., words of increasing length and morphological structure (e.g., response- responsible- responsibility, or sentences of increasing length and structure 'the girl hit the boy'- 'the girl with the blue hat hit the boy'- 'the girl with the blue hat hit the boy' the girl with the blue hat hit the boy with the yellow sweater'). Ten triplets of words or sentences will be used as trained materials and another 10 triplets as untrained materials (evaluated at the beginning and end of treatment as well as at follow-up intervals). The treatment will involve the use of several steps which will progressively induce the patient to correctly reproduce the whole stimulus. In the beginning, the clinician speaks the whole stimulus and asks the patient to repeat it. If the patient correctly repeats the stimulus, the clinician would move on the next step. In the next step, the clinician speaks the stimulus with a pause between each syllable— or word in the case of sentences—prolongs the vowel sound, exaggerates the articulatory gestures and

asks the patient to do the same. The clinician repeats this step 3 times. If the participant succeeds, s/he is asked to repeat the stimulus 20 times without help. If the patient is not able to articulate the stimulus in the last step, the response is considered as an error. In this way we will be able to evaluate the performance and the progress of the participants for both the trained and untrained stimuli.

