## c. Statistical plan including sample size justification and interim data analysis.

Design. This is a crossover trial, where each participant will be randomly assigned to receive either "IFG tDCS, then sham then SMG (in case a second stimulation site is implemented)" (group1) or "SMG then sham then IFG" or "sham then IFG then SMG". In case a second stimulation site is not implemented participants will receive either sham and then tDCS (group 1) or tDCS and then sham (group 2). Based on previous studies regarding long-term effects of tDCS (see Fiori et al., 2011; Fridriksson et al., 2011; both looking at 3-weeks post-stimulation in participants with aphasia) and given the degenerative nature of PPA (and some cases of MCI), we assume that even though the effect of tDCS on the absolute level of the outcome may or may not persist at 2 weeks, the effect on the rate of decline persists no longer than 2 weeks. Analyses. The primary analyses will be a robust type of repeated measures Multivariate ANCOVA. Specifically, for each subject (i) and at follow-up times t=immediately after treatment, then 2 weeks and 2 months, we will consider the data  $IFG_{ti}$ ,  $SMG_{ti}$ , and  $S_{ti}$ ; here,  $IFG_{ti}$  is the change of outcome from just before IFG tDCS treatment to time t after IFG tDCS treatment for subject i; and similarly for SMGt,i, and St,i for IFG tDCS and sham. For the behavioral methods, change of outcome is considered the difference (before and after therapy) of the independent measure of initial letter-sound associations learned. Then the research hypothesis that IFG (or SMG) treatment is superior to sham will be tested by testing the hypotheses that the distribution  $pr(R_{ij} - S_{t,i})$  (or  $pr(L_{t,i} - S_{t,i})$ ) is not centered at zero. This will be done nonparametrically by obtaining the latter null distributions by the random permutation of the treatment labels (IFG, S, SMG) of the data for each patient (Rosenbaum, 1988). The design effect, i.e., the ratio of sample sizes needed by an independence design vs. the crossover design to achieve a given power, depends on the correlations of outcomes across times and treatments. We have calculated that this crossover design with 30 participants and design effect of 1.5 has power 75% to detect an effect size of 0.8 between a tDCS site and sham treatment. In secondary analysis, we will use regression to examine if any effects of tDCS vary across participants with different characteristics such as age and atrophy volume. The present design allows us to evaluate the language and neuromodulatory effects of both IFG and SMG stimulation as well as language therapy alone (in the condition of sham stimulation).

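### Only the lexical spelling stream gives each crossover condition its own trained set; elsewhere block 2 may retrain block 1 items, which costs power and, if retention differs by condition, biases the tDCS-sham contrast

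*Combined protocol and SAP*

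**What the plan says.** The protocol's section 3a describes the stimuli stream by stream.

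- **Lexical spelling:** three matched sets of ten, rotated by condition. "Set 1 will serve as trained items for the first condition (either sham or tDCS), and set 2 as untrained items"; set 2 is then trained in the next condition, with set 3 as its untrained comparison.
- **Repetition:** "Ten triplets of words or sentences will be used as trained materials and another 10 triplets as untrained materials". No further set is named and neither set is tied to a condition.
- **PGC spelling:** "Up to 30 English sounds will be selected representing most common word-initial English phonemes". Material is taught in blocks of ten, and the participant moves on at 80% correct. The pool is not divided by condition.
- **Naming Level 2 (category cards):** every category on the cards counts as trained, and cards get harder over time. "Untrained categories will not be used in this training", but the trained cards are not split between conditions.
- **Naming Level 1:** trained stimulus sets are mentioned in the plural, with no link to a condition.
- **Computerized therapy:** tasks are chosen from a programme, and no item set is defined.

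Section 3b puts about 2 months between blocks. Section 6a makes change on trained items a primary outcome. Section 6c measures change from just before each treatment, names letter-sound associations (the PGC material) as the behavioural measure, and tests by permuting treatment labels within each patient. It names no period or sequence term.

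**The concern.** A gain score depends on the room left to improve. If block 2 uses items taught in block 1 and some of that learning survives the gap, block 2 starts higher and its gain is smaller, whichever condition comes second. The within-patient tDCS-sham difference is then pushed up in patients who had tDCS first and down in those who had sham first. A test with no period term treats that split as noise.

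The plan's own expectations make retention plausible. Hypothesis 1b expects combined-therapy gains to last 2 and 6 months, which reaches or outlasts the gap, and expects gains from behavioural therapy alone not to last. Section 6c limits only the effect on rate of decline to 2 weeks and leaves open whether the effect on level persists. Unequal retention is the worse case, because the shifts in the two orders no longer cancel.

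If staff avoid reuse by choosing new material as they go, the items in the two blocks are unmatched, and on the category cards harder, so item difficulty is confounded with period.

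**Working it through.** **1. The plan's power figure.** Section 6c takes 30 participants and a design effect of 1.5, and claims that the crossover "has power 75% to detect an effect size of 0.8 between a tDCS site and sham treatment". Its design effect is "the ratio of sample sizes needed by an independence design vs. the crossover design to achieve a given power", so 30 × 1.5 = 45 independent participants, or 22.5 per arm. Alpha is not stated; I assume 0.05 two-sided. Then z = 0.8 × √(22.5/2) − 1.96 = 2.683 − 1.960 = 0.723, giving 76.5% (74.6% by noncentral t). The stated 75% reproduces.

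**2. Block 2 loss on the plan's own scale.** Those inputs imply a variance of 4 × 30/45 = 2.667 for the within-patient difference D, in squared outcome SDs. If the mean block 2 gain is lower by π SDs, D shifts by +π in one order and −π in the other. Its mean is unchanged under 1:1 orders, and its variance as seen by an unadjusted test is 2.667 + π². Power is Φ(0.8√30/√(2.667 + π²) − 1.96). The documents give no value for π.

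| Assumed π | Power |
|---|---|
| 0 | 76.5% |
| 0.5 | 72.8% |
| 1.0 | 62.9% |
| 1.5 | 50.6% |

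**3. A retention model.** All inputs are assumed: start 40% correct; tDCS closes 2/3 and sham 1/2 of the remaining gap; error SD 8 per score; 15 patients per order; equal retention r of block 1 gains.

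- Separate sets: gains of 40 and 30 points, true difference 10.
- Reused set, tDCS first: 40 − ½(60 − 40r) = 10 + 20r.
- Reused set, sham first: ⅔(60 − 30r) − 30 = 10 − 20r.
- At r = 0.7 these are +24 and −4, with mean 10.

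Four scores enter D, so its error SD is √(4 × 64) = 16, and the mean has SE 16/√30 = 2.92. The unadjusted test estimates its SE as √[(256 + (20r)² × 30/29)/30], so power is about Φ[(10 − 2.045 × estimated SE)/2.92].

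| Retention | Estimated SE | Power |
|---|---|---|
| Separate sets | 2.92 | 91% |
| 30% | 3.13 | 89% |
| 50% | 3.46 | 84% |
| 70% | 3.91 | 75% |
| 90% | 4.44 | 62% |

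The separate-sets entry uses the noncentral t. In this model a period-adjusted analysis keeps about 91% at every retention level.

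**4. An item-level check.** A simulation of the sign-flip permutation test assumed 10 items, 30% baseline, and learning probabilities of 0.50 (sham) and 0.71 (tDCS), with between-patient variation. The mean contrast stayed at about 12 points throughout.

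| | Power, no period term | Power, period term |
|---|---|---|
| Separate sets | 76% | 79% |
| 25% retention | 79% | 85% |
| 50% | 62% | 76% |
| 75% | 46% | 68% |
| 90% | 36% | 64% |

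There is no loss at low retention. At high retention the period term recovers only part of it.

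**5. Unequal retention.** In the model of step 3, with retention r_T after tDCS and r_S after sham, the order means are 10 + 20r_T and 10 − 20r_S. Their average is 10 + 10(r_T − r_S).

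- 70% versus 0%: 10 + 7 = 17.
- 70% versus 30%: 10 + 4 = 14.

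The true difference is 10 in both cases. A period-adjusted estimate is this same average of the two order means, so a period term does not remove the bias.

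**The case against.** The strongest reply is that reuse is inferred from silence. A reader might conclude that every stream outside lexical spelling has one trained set and that block 2 always repeats it. The documents do not support that. Naming Level 1 and the Assessment paragraph both speak of trained sets in the plural, and the latter includes sentences. Participants who have not finished the PGC pool may begin block 2 on new sounds. Category cards move on to harder material. Computerized therapy defines no items at all. Even the repetition sentence could mean ten triplets per treatment. This stands as a limit on scope: literal reuse follows only from the repetition text, and elsewhere the allocation is simply not stated.

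Second, section 3a (Analyses) cites preliminary data for a small carry-over effect. It gives no figure, so it cannot be set against Hypothesis 1b.

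Third, with equal retention and balanced orders the harm is lost precision, and a missing period term accounts for much of it. That is right, and the fix therefore includes one. It does not answer the unequal-retention case.

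Fourth, splitting the PGC pool has a real price. Suppose SD 8 applies to 20 trained sounds and error scales with 1/√items. Ten sounds then give SD 8√2 = 11.3, an SD of 22.6 for D, SE 22.6/√30 = 4.13 and power of about 65%, close to what reuse gives at 90% retention. This stands as a cost to precision. It is not a reason to accept a contrast that differential retention can bias.

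**Conclusion.** The point holds in a limited form. Lexical spelling is the only stream that assigns a matched trained set to each condition. Repetition, read literally, retrains the same ten triplets. PGC, which supplies the measure named in section 6c, and the category cards leave open whether block 2 meets learned items or unmatched new ones. Naming Level 1 ties none of its sets to a condition.

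If items are reused with equal retention, the contrast stays centred and power falls, materially from about 50% retention upward. If retention is greater after tDCS, as Hypothesis 1b predicts, the contrast is inflated even with equal orders. Every size given rests on assumed learning rates, error and retention, because the documents supply none. The gap-to-100% model also fits accuracy scores better than names produced in one minute.

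It would go too far to say that the trial's contrast is biased or that its power is lost: that depends on how items are allocated in practice and on retention. I rate this as an important recommendation rather than a mandatory correction. It is best settled before further participants start block 1, since overlap cannot be undone for a participant afterwards.

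**What to change.** Extend the lexical rotation to the repetition, PGC and naming streams, with one or two sentences in each:

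- Before block 1, define matched, disjoint sets for condition 1, condition 2 and never trained: a third set of triplets, category cards split by difficulty-matched halves, picture sets for Level 1, and PGC sounds allocated in advance. Where section 6c's second stimulation site is used, add one more set.
- Assign sets to conditions at random.
- Do not let a participant who reaches criterion advance into the set reserved for the other condition.
- Include period in the primary analysis in section 6c, for example by averaging the two order-specific mean differences, with a matching permutation scheme.

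The cost is item preparation, a few protocol sentences, and fewer trained PGC sounds per condition, which makes each PGC score less precise; the sample-size statement should allow for that. Disjoint sets remove only the carry-over held in retained items. Any general skill carried into block 2 would remain.
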